Further analysis of all T-Guard patient outcomes as combined across all studies including Phase 1/2/3 trials and the Expanded Access Program, and inclusive of the three deaths on the BMT CTN 1802 protocol, suggests that T-Guard could provide a new and more effective therapeutic option for patients that currently have very few approved options. The efficacy evaluation now includes 35 SR-aGVHD patients, of whom 15 (42.8%) had a Complete Response (CR) and 6 (17.1%) a Partial Response, yielding an Overall Response Rate (ORR) of 60.0%, with a 6-month OS of 60% (including the BMT CTN 1802 participants). These results compared favorably with higher Day 28 CR rate (historical control of 34.4%), similar to the ORR of 62.3%, and higher than the 6-month OS as reported in the REACH2 trial of 48.7% (Zeiser, NEJM 2020). The high D28 CR rate with T-Guard appears to be especially (or particularly) promising as CR at D28 is the strongest correlate with long term survival. Thus, in consultation with the FDA, BMT CTN 1802 was closed to pursue the randomized clinical trial design with ruxolitinib in Grade III-IV SR-aGVHD to be studied in current trial. The experience from BMT CTN 1802 has helped clarify inclusion/exclusion criteria and safety monitoring for this randomized trial. The randomization may also help determine if the toxicities observed in the single arm study may have been associated with T-Guard administration or if they are inherent to the very high-risk population eligible for SR-aGVHD trials.

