4.4.4 Required Adverse Event Reporting

The required adverse event reporting for the BMT CTN 2002 protocol is outlined below.

- T-Guard arm: all adverse events, including SAEs, must be reported from randomization through 30 days following the last dose of T-Guard.
- Ruxolitinib arm: all adverse events, including SAEs, must be reported from randomization through Day 44 (to align with the maximum reporting period for participants in the T-Guard arm).
- Any SAEs occurring after that period, but assessed as related to the investigational product, must be reported.
- Any unanticipated SAEs from time of enrollment through the study defined follow-up are required to be reported..
- Any grade 4 anticipated event not collected on the calendar-driven toxicity or specified event-driven form must **also** be reported.
- Special Situations and Adverse Events of Special Interest (AESIs) must be reported from randomization through the study defined follow-up period.

- Grade 1 CMV infections, as defined in Appendix G, requiring treatment should be reported from randomization through the study defined follow-up period.

SAEs that require reporting will be reported through an expedited AE reporting system via the EDC system. **All SAEs, Special Situations, and AESIs must be reported within 24 hours of knowledge of the event.** Events entered in EDC will be reported using NCI's CTCAE Version 5.0. If there are network outages, a paper copy of the AE form must be completed and emailed to Emmes to initiate Sponsor review. Once the system is available, the event information must be entered into the system.

The Sponsor has a list of events classified as Special Situations. These events are 1) medication error, 2) overdose and 3) pregnancy. These events must be reported, regardless of grade or seriousness, following the reporting process for SAEs.

The Sponsor has a list of AESIs to be reported. These events include any grade of 1) TMA, 2) CRS, 3) CLS, 4) Myalgia, or 5) CK elevation and 6) grade 3 or higher cytopenias. These events must be reported, regardless of grade or seriousness, following the reporting process for SAEs.

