5.1.2 Randomization and Blinding

Participants will be randomized at the time of enrollment in a 1:1 ratio to the treatment arms. Randomization will be stratified by center region (US vs. Europe) and age group (at least 55 years vs. under 55). Stratified treatment assignments will be generated using permuted blocks of random sizes.

As this is an open-label trial, no blinding will be performed.

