5.1.5 Sample Size and Power Considerations

Data on participants with Grade III-IV SR-aGVHD were examined from three previous T-Guard studies in a meta-analysis: the Phase 1/2 study (XenTG001), an Expanded Access Program for this study (Named Participants), and the Phase 3 study BMT CTN 1802. Estimates of Day 28 CR rates for each cohort and for the combined participant populations are displayed in [Figure 5-1](#). Aggregating data from these 30 participants gives an estimated CR rate under T-Guard treatment of 43.3% (95% CI: 27.1% - 61.2%). Among the 101 Grade III-IV SR-aGVHD participants in the ruxolitinib arm of the REACH2 trial, the CR rate was 25.7% (95% CI: 18.2% - 35.1%). These data suggest Day 28 CR rates of approximately 43% and 26% for T-Guard and ruxolitinib, respectively.

Figure 5-1: Day 28 CR Rates from Meta-analysis of Previous T-Guard Trials

The primary hypothesis will be evaluated by comparing the proportion of participants attaining a Day 28 CR in each arm, aiming to detect an improvement for T-Guard treatment over ruxolitinib. If the true CR rates for T-Guard and ruxolitinib match the respective rates of 43% and 26% seen in previous studies, the difference in rates is 17% favoring T-Guard. With the inclusion of interim analyses for efficacy and futility as detailed in Section 5.2, 246 participants are required to detect this difference with 80% power and a one-sided type I error rate of 2.5%. The pivotal analysis will also adjust for the stratification factors used for randomization. This practice is known to increase statistical power beyond that of an unadjusted two-arm comparison (Kahan and Morris 2012), so 80% is a conservative estimate of the true power.

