5.6.12 Incidence of Toxicities

The frequency of Grade 3-5 toxicities per CTCAE Version 5 occurring from randomization until 56 days post-randomization will be tabulated by organ system for each treatment arm. The maximum severity of reported toxicities during that period will also be summarized. The proportions of participants reporting Grade 3-5 toxicities through Day 56 will be compared between arms using logistic regression with adjustment for the stratification factors and for acute GVHD grade at randomization (Grade III vs. IV).

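### Section 5.6.12 compares the arms only on an overall Grade 3-5 toxicity proportion, which is insensitive to one specific toxicity, and apart from TMA no event of special interest has a planned between-arm estimate

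*Combined protocol and SAP*

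**What the plan says.** Section 5.6.12 gives three outputs for Grade 3-5 toxicity from randomization to Day 56. Frequencies "will be tabulated by organ system for each treatment arm", maximum severity is summarized, and one comparison is named: "The proportions of participants reporting Grade 3-5 toxicities through Day 56 will be compared between arms using logistic regression", adjusted for the stratification factors and aGVHD grade. The sentence does not say whether the regression is overall or per organ system. No significance level, sidedness, power or target difference is given.

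Section 4.4.4 lists the events of special interest: "any grade of 1) TMA, 2) CRS, 3) CLS, 4) Myalgia, or 5) CK elevation", and Grade 3 or higher cytopenias. They are reported in both arms throughout follow-up. In Chapter 5 only TMA from this list has a between-arm analysis (5.8.7, exploratory, Gray's test).

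Section 1.3.1.2.4 gives a reason for having a randomized control: "The randomization may also help determine if the toxicities observed in the single arm study may have been associated with T-Guard administration", or whether those toxicities belong to the high-risk population.

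**The concern.** The attribution question in 1.3.1.2.4 concerns particular toxicities. Section 1.3.1.2.3 names the class risks as vascular leakage, myalgia with CK rise, and cytokine release. The regression in 5.6.12 reduces each participant to yes or no on any Grade 3-5 toxicity. A participant who would have had some other severe event anyway counts the same with or without a T-Guard toxicity. When most participants already have a severe event, an excess of one toxicity barely moves the proportion.

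At stake is the interpretation of a null result. A non-significant odds ratio could be taken as similar toxicity when a specific excess is present, and the plan provides no interval that would show how large an excess remains compatible with the data.

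**Working it through.** **Inputs from the documents.**
- 246 participants (5.1.5), and "Participants will be randomized at the time of enrollment in a 1:1 ratio to the treatment arms", so 246 / 2 = 123 per arm.
- Table 1-3 (REACH2, to Day 28), ruxolitinib versus control: any Grade 3 or higher event 118/152 versus 117/150; Grade 3 or higher thrombocytopenia 41/152 versus 23/150.

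**Assumptions, because the documents are silent.** Two-sided 5%; background composite rate p0 of 60%, 78% or 90%; an added T-Guard toxicity of rate x, independent of other severe events; a control rate of 2% or 5% for the specific toxicity.

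**Step 1. The plan's own figure.** No power is stated for the toxicity comparison. As a check on method, simulating the primary comparison (43% versus 26%, boundaries 2.6562 and 1.9817, futility at 4 of 23) gives 80.5% power with an unpooled z statistic. Table 5-2 states 80.56%.

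**Step 2. The protocol's own example.** Unpooled 95% intervals for differences, pooled z for p-values:
- Any Grade 3 or higher event: 77.6% − 78.0% = −0.4 points (95% CI −9.7 to 9.0), p = 0.94.
- Grade 3 or higher thrombocytopenia: 27.0% − 15.3% = 11.6 points (95% CI 2.5 to 20.8), p = 0.013.

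A difference of about 12 points in one severe event left no trace in the composite. This step needs no assumption about background or independence.

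**Step 3. Power of the composite.** The T-Guard rate is pT = 1 − (1 − p0)(1 − x). For p0 = 78% and x = 15%: 1 − 0.22 × 0.85 = 81.3%, a shift of 3.3 points. Power is by exact enumeration of the pooled two-proportion z test, 123 per arm:

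| Assumed background p0 | x = 10% | x = 15% | x = 20% |
|---|---|---|---|
| 60% | 10% | 17% | 26% |
| 78% | 7% | 10% | 14% |
| 90% | 6% | 7% | 8% |

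At p0 = 78%, x has to reach about 58% before power is 80%.

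**Step 4. The same toxicity tested directly**, with the same formula applied to the control rate, x = 15%:
- Control 2%: 1 − 0.98 × 0.85 = 16.7%; power 99%.
- Control 5%: 1 − 0.95 × 0.85 = 19.25%; power 95%.

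**Step 5. Without independence.** If the added toxicity falls on participants with no other severe event, the composite moves more. For 78% versus 88% power is 56%, so 44% of such excesses would be missed.

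**The case against.** The case against has real force on several points.

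- *A reader might infer that this is the trial's only between-arm safety test.* It is not. Section 5.8.7 compares TMA, 5.8.2 and 5.8.3 compare CMV and EBV events, and 5.3.2 monitors Day 60 mortality between arms. The point is limited to 5.6.12 and to the events of special interest other than TMA.
- *A reader might infer that the composite sits near its ceiling and that a large toxicity is missed about 90% of the time.* The documents do not support this. The 78% is a REACH2 rate of any adverse event, including infections, which this trial records separately (4.4.4). It covers 28 days rather than 56, and a broader population: 5.1.5 refers to "Among the 101 Grade III-IV SR-aGVHD participants in the ruxolitinib arm of the REACH2 trial", out of 154 assigned. These differences push in opposite directions, so the Day 56 rate here is unknown. A 90% miss rate follows only from the assumed 78%, 15% and independence.
- *A reader might take CLS in 8 of 20 patients (Table 1-1) as evidence of a severe excess.* That count is any grade. Table 1-2 lists potentially related CLS once, at Grade 2.
- *Equal composites in REACH2 do not prove that a composite cannot discriminate.* Some severe events were more frequent with control (hypoalbuminemia 10/150 versus 6/152), so offsetting is possible. This stands, but offsetting is itself a reason to look at specific events.
- *The objective is descriptive, and the counts by arm let a reader derive a difference.* This is true for organ systems. Nothing in 5.6.12 or elsewhere in Chapter 5, however, plans a tabulation or an interval for the non-TMA events of special interest as such.
- *The regression may be meant per organ system.* The wording allows it. Every composite figure above depends on the overall reading, and the ambiguity should be removed in either case.

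**Conclusion.** The concern holds in this form: the one comparison in 5.6.12, read as overall, is a poor instrument for detecting a specific toxicity, and five of the six events of special interest in 4.4.4 have no planned between-arm estimate, although 1.3.1.2.4 looks to randomization to help attribute the earlier toxicities.

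For an assumed independent 15% added toxicity, power is about 7% to 17% across assumed backgrounds of 90% down to 60%, against 95% to 99% for a direct comparison over a 5% or 2% control rate. The low sensitivity therefore does not require a background near 100%. It does weaken if the toxicity concentrates in participants with no other severe event (about 56% power for 78% versus 88%). The background, the size of the added toxicity, the independence, the control rates and the two-sided 5% level are all assumptions. The Table 1-3 contrast is the only part resting on documented data alone, and it illustrates the problem without giving a rate for this trial.

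This is a gap in the safety analysis and its reporting. It does not affect the primary efficacy inference.

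**What to change.** In 5.6.12:
1. State that the logistic regression is on any Grade 3-5 toxicity overall, and keep it as a summary.
2. For each event of special interest in 4.4.4, and for Grade 3-5 toxicity within each organ system, report through Day 56 the between-arm risk difference with a two-sided 95% confidence interval, using an exact method where events are sparse. Label these as estimation without multiplicity adjustment.
3. State that a non-significant composite is not evidence of equal safety, and that the upper confidence limit for each specific event shows the excess that has not been excluded.
4. Note beside the CK result that CK after screening is measured only when there is muscle pain (2.5.1.6, Appendix K), so that comparison reflects symptom-triggered testing.

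The cost is SAP wording and a few tables from data already collected in both arms. The downside is a set of unadjusted intervals, some of which will exclude zero by chance; the label in item 2 makes that plain.

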5.6.13 Subgroup Analyses of Day 28 CR Rate

In a secondary analysis of the primary endpoint, the CR rate at Day 28 post-randomization will be described for each age group (55 years or over vs. under 55), gender, race, ethnicity, center region (US vs. Europe), and aGVHD grade (III vs. IV). Sample proportions and 95% Wilson score or Clopper-Pearson CIs will estimate the Day 28 CR rate of each subgroup by treatment arm. For each subgroup, the difference in CR rates between arms will be described using a point estimate and 95% CI.

5.7 ANALYSIS OF PHARMACOKINETIC / PHARMACODYNAMIC ENDPOINTS (T-GUARD ONLY)

The analysis of pharmacokinetic / pharmacodynamic endpoints will be based on the PK analysis population.

5.7.1 Pharmacokinetics

A population pharmacokinetic model will be developed for T-Guard based on the SPV-T3a-RTA and WT1-RTA levels measured in samples obtained before each infusion and at pre-defined timepoints after infusion (see [Table K-1](#)). The model will be used to evaluate the following metrics:

- C_{inf} : Observed and model-predicted concentration at the end of infusion
- CL: Systemic clearance
- AUC: Model-predicted area under the curve from the start of the current infusion until the next infusion or until 48 hours following for the last infusion
- $t_{1/2}$: Model-predicted terminal half-life
- Vc: Volume of the central compartment

Additionally, the impact of various factors on these measures will be evaluated, including age, weight, BSA, BMI, disease status, and ADA.

5.7.2 Immunogenicity

ADA responses in the form of anti-SPV-T3a-RTA and anti-WT1-RTA antibodies will be evaluated using serum samples obtained at baseline and at Days 6, 14, 28, 90, and 180 following initiation of T-Guard treatment. Antibody levels will be described using descriptive statistics at each time point. Changes in levels from baseline will be evaluated using Wilcoxon signed rank tests.

5.8 ANALYSIS OF EXPLORATORY ENDPOINTS

The analysis of exploratory endpoints will be based on the ITT analysis population.

5.8.1 Discontinuation of Systemic Steroids

The proportion of participants that is free of systemic steroids at Day 180 post-randomization will be described by treatment arm using sample proportions and 95% Wilson score or Clopper-Pearson CIs. The proportions of steroid-free participants at Day 180 will be compared between arms using Barnard's exact test.

5.8.2 CMV Reactivation

Among participants who were CMV positive at enrollment, the cumulative incidence of initiation of systemic treatment for CMV-reactivation will be described for each treatment arm using the Aalen-Johansen estimator, with death treated as a competing risk. Estimates and 95% CIs of the cumulative incidence of CMV reactivation will be provided at Day 180 post-randomization. The cumulative incidence of CMV will be compared between arms using Gray's test.

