5.6.6 Non-relapse Mortality (NRM)

NRM is defined as death from any cause other than malignancy relapse/progression. The time from randomization until NRM will be described for each treatment arm using the Aalen-Johansen estimator, with malignancy relapse/progression treated as a competing risk. Estimates and 95% CIs of the cumulative incidence of NRM will be provided at Days 100 and 180 post-randomization. The cause-specific hazards of NRM will be compared between arms using a Cox proportional hazards model with adjustment for the stratification factors and for acute GVHD grade at randomization (Grade III vs. IV).

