5.8.3 EBV-associated Lymphoproliferative Disorder

The cumulative incidence of either EBV-associated lymphoproliferative disorder or EBV reactivation requiring therapy with rituximab will be described for each treatment arm using the Aalen-Johansen estimator, with death treated as a competing risk. Estimates and 95% CIs of the cumulative incidence of EBV-associated lymphoproliferative disorder/EBV reactivation will be provided at Day 180 post-randomization. The cumulative incidence of EBV-associated lymphoproliferative disorder/EBV reactivation will be compared between arms using Gray's test.

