5.8.7 Thrombotic Microangiopathy (TMA)

The frequency of TMA events will be tabulated for each treatment arm. The cumulative incidence of TMA will be described by arm using the Aalen-Johansen estimator, with death treated as a competing risk. Estimates and 95% CIs of the cumulative incidence of TMA will be provided at Day 28 post-randomization. The cumulative incidence of TMA will be compared between arms using Gray's test.

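### CMV, EBV and TMA are compared between arms only by unadjusted Gray's tests, which mix the effect on the event with the effect on death; an adjusted cause-specific comparison should be added

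*Combined protocol and SAP*

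**What the plan says.** The three between-arm comparisons are:

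- CMV (5.8.2): "The cumulative incidence of CMV will be compared between arms using Gray's test".
- EBV (5.8.3): "The cumulative incidence of EBV-associated lymphoproliferative disorder/EBV reactivation will be compared between arms using Gray's test".
- TMA (5.8.7): "The cumulative incidence of TMA will be compared between arms using Gray's test".

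Each endpoint is estimated by the Aalen-Johansen method with death as a competing risk. No strata or covariates are named for any of the tests. CMV and EBV are read at Day 180 (for CMV: "Estimates and 95% CIs of the cumulative incidence of CMV reactivation will be provided at Day 180 post-randomization"). TMA is read much earlier: "Estimates and 95% CIs of the cumulative incidence of TMA will be provided at Day 28 post-randomization". Section 5.8 opens with "The analysis of exploratory endpoints will be based on the ITT analysis population", but the CMV analysis is restricted: "Among participants who were CMV positive at enrollment". The number of such participants is not given.

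The secondary endpoints with competing risks are handled differently. For non-relapse mortality, section 5.6.6 says "The cause-specific hazards of NRM will be compared between arms using a Cox proportional hazards model with adjustment for the stratification factors", and it also adjusts for aGVHD grade. Time to CR (5.6.3), chronic GVHD (5.6.9) and relapse (5.6.10) follow the same pattern. The exploratory EASIX analysis (5.8.8) also models a cause-specific hazard, so exploratory status alone does not explain the difference. Section 5.6.11 describes infections and treated CMV to Day 90 by arm, without a between-arm test.

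**The concern.** Gray's test compares cumulative incidence functions. In effect, a participant who dies without the event stays in the comparison as someone who never has it. An arm with more deaths therefore accumulates fewer events even when the event rate among those alive is the same or higher. An arm with fewer deaths accumulates more.

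This matters because the plan regards a mortality difference as possible in either direction. Section 5.3.2 monitors for excess Day 60 deaths on T-Guard, and section 1.4 hopes for better survival. The first three participants in the preceding single-arm Phase 3 trial died of infection or sepsis within 30 days (1.3.1.2.4), and TMA is an event of special interest (4.4.4). Section 1.3.1.2.4 also says that randomization may help show whether earlier toxicities came from T-Guard or from the underlying risk of the population. For CMV, EBV and TMA, that question concerns the event rate among participants still alive. No planned between-arm comparison of these three endpoints addresses it.

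**Working it through.** **Plan figure.** The documents give no power or effect size for these three comparisons. The nearest stated figure is the excess-mortality scenario in section 5.3.2, Day 60 mortality of 65% versus 40%. Its odds ratio is (0.65/0.35)/(0.40/0.60) = 2.786, which agrees with the stated 2.79.

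**Inputs for the CMV illustration.**
- Ruxolitinib mortality at Days 30/60/180 is 17.5%, 40% and 51.3%. The first is the midpoint of the expected 15-20% and the second is the expected rate (both 5.3.2). The third is 100 − 48.7, from the REACH2 six-month survival in 1.3.1.2.4, which is not specific to Grade III-IV.
- T-Guard mortality is 25%, 50% and 60% (assumed).
- CMV cumulative hazard on ruxolitinib at the same days is 0.75 × (0.30, 0.40, 0.45) = 0.225, 0.300, 0.3375 (assumed, mostly early). The T-Guard values are 1.8 times these: 0.405, 0.540, 0.6075.
- Event and death times are independent, with administrative censoring only. Tests are two-sided at 5%, because the plan gives no level.

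**Cumulative incidence.** In an interval with event hazard increment a, death hazard increment b and event-free survival S at its start, the incidence added is S × a/(a+b) × (1 − exp(−(a+b))). Death increments are differences of −ln(1 − mortality).

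| Arm and mortality | Days 0-30 | Days 30-60 | Days 60-180 | Day 180 CMV |
|---|---|---|---|---|
| Ruxolitinib | 0.184 | 0.041 | 0.015 | 24.0% |
| T-Guard, ruxolitinib mortality | 0.305 | 0.060 | 0.021 | 38.5% |
| T-Guard, 25/50/60% mortality | 0.292 | 0.052 | 0.017 | 36.1% |

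For the last row, the first interval has a = 0.405 and b = −ln(0.75) = 0.288, giving (0.405/0.693) × (1 − exp(−0.693)) = 0.292. The hazard ratio is 1.8 in both T-Guard rows, but the difference from ruxolitinib shrinks from 14.5 to 12.1 points solely because more T-Guard participants die.

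**Chance of a significant CMV excess on T-Guard** (simulated; cause-specific log-rank versus subdistribution log-rank, which is Gray's test when censoring is only administrative):

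| Day 60 mortality, T-Guard/ruxolitinib | Per arm | Cause-specific | Gray |
|---|---|---|---|
| 40/40% | 123 | 69% | 68% |
| 50/40% | 123 | 72% | 57% |
| 50/40% | 75 | 51% | 39% |

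Repeat runs agree within about 3 points. The 123 is 246/2. The 75 stands for an unknown number CMV positive at enrollment.

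**Opposite direction.** With equal CMV hazards (0.30, 0.40, 0.45 in both arms) and T-Guard mortality of 15%, 32% and 40%, the same formula gives 0.240 + 0.054 + 0.021 = 31.5% on T-Guard and 0.237 + 0.050 + 0.018 = 30.5% on ruxolitinib. The shift is one point.

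**EBV.** Assume constant hazards, 10% incidence by Day 180 on ruxolitinib, hazard ratio 2 and 123 per arm. Power is 51% cause-specific versus 48% Gray at equal mortality, and 50% versus 27% at 50/40%.

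**TMA to Day 28.** Take Day 30 mortality of 30% (the plan's unacceptable rate) versus 15%, at 123 per arm. With an assumed 10% base rate, power is 51% cause-specific versus 41% Gray at hazard ratio 2, and 94% versus 88% at hazard ratio 3. With a 5% base rate it is 30% versus 24% and 69% versus 61%.

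**The case against.** The main objection is that Gray's test is the right test for the stated aim. Section 2.3.3 sets out to estimate the incidence of these events, and Gray's test compares cumulative incidence. The endpoints are exploratory and carry no alpha. This stands: the test is incomplete here, not wrong. It also disposes of one tempting inference, that a rejection under equal event hazards but unequal mortality is a false signal of infection harm. In that case the cumulative incidences truly differ, and the test reports a real difference in burden per participant.

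A second objection is that excess mortality would be noticed anyway. At 65% versus 40%, Table 5-5 gives a 95.9% chance of a monitoring trigger, and the mean deaths in Table 5-6 imply about 34 per arm (22.3/0.65 and 13.7/0.40). Power figures at 123 per arm for that scenario would therefore mislead. The point is weaker at 50% versus 40%, where the trigger probability is 40.3%. The mean deaths there imply about 87 per arm (43.7/0.50 and 35.0/0.40), at which power is about 56% cause-specific versus 43% Gray. Triggers prompt DSMB review and do not force closure (5.3). Worse survival also does not show whether infection risk rose.

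A reader might infer that these safety questions were singled out for weaker methods. The documents do not support that. Unadjusted tests are common in section 5.8 (Barnard's test in 5.8.1, rank sum tests in 5.8.4 and 5.8.6), and toxicities receive adjusted logistic regression (5.6.12).

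A reader might also infer that an excess would be hidden. That is too strong. Masking is partial at a ten-point mortality gap and small for TMA, whose events are also tabulated by arm, reported as events of special interest and reviewed by a blinded panel (3.5.1.7). Overall survival is reported by arm.

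**Conclusion.** The point holds as a cheap improvement. For CMV and EBV to Day 180, the planned tests cannot separate an effect on the event from an effect on death. In the CMV illustration at 50% versus 40% Day 60 mortality, Gray's test loses about 15 points of power at 123 per arm and about 12 at 75. At equal mortality it loses about one. For TMA at Day 28 the loss is about 5 to 10 points even at the plan's unacceptable Day 30 mortality.

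These sizes depend on assumptions: the CMV time course, the T-Guard mortality curve, the EBV and TMA base rates, and independence of event and death times. The ruxolitinib CMV curve gives 0.539 × (1 − exp(−0.417 × 28/30)) = 17% by Day 28, against 26% for ruxolitinib in REACH2 (1.3.2.1, a population that includes lower-grade disease). If CMV risk stayed high to Day 180 the loss would be larger, but the documents give no support for such a curve, so no conclusion rests on it.

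**What to change.** In sections 5.8.2, 5.8.3 and 5.8.7, add the cause-specific Cox comparison already specified in 5.6.6, 5.6.9 and 5.6.10, adjusted for region, age group and aGVHD grade. Where events are too sparse for the model, use a log-rank test stratified by region and age group. Beside each Aalen-Johansen curve, show the cumulative incidence of death without the event, by arm. Keep the Aalen-Johansen estimates and Gray's test as the comparison of cumulative incidence, and state which question each test answers.

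The cost is a few lines of text and three extra exploratory model fits on data already collected. The downside is a second p-value for each endpoint. Settling this before the arms are compared avoids a later choice between two tests that disagree.
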